Participant Status	Is the patient being managed with extracorporeal membrane oxygenation?
	Is the patient being managed with extracorporeal CO2 (ECCO2R) removal?
	What is the GI index?
LAB ABGS	PH
	Base excess

The critical components RAP indicated sites may re-consent subjects recruited under protocol amendment #1 and enter any new data into the eCRF and suggested an approach for imputing missing data. However, the missing data approach described in the critical components RAP may not be appropriate to the individual subject's circumstances and so the default will now be to leave any data as missing/not applicable. Only 2x subjects were recruited under protocol amendment #1 (PPD and PPD) so the impact of leaving their data missing/not applicable is unlikely to be influential on the outcome, and following the early termination decision these exploratory endpoints are not going to be analyzed further.

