Subject	INOX	Inhaled Nitric Oxide at any time (Binary Y/N)	DMDATA.FACM (Where FCMTSTCD=FCMAX001) Set to Y if Any of FCMORSCD = ZZY for a subject; Set to N otherwise
Time	INOI	Inhaled Nitric Oxide by Study Day (Binary Y/N)	DMDATA.FACM (Where FCMTSTCD=FCMAX001) Treat any Screening results as being from Day 1 (use the worst case outcome as Day 1 result). For each subject and visitnum match: Set corresponding INOI to Y if FCMORSCD = ZZY for Day ; Set to N otherwise
Subject	VASOX	Vasopressor, Inotrope or other Vasoactive agent at any time (Binary Y/N)	DMDATA.FACM (Where FCMTSTCD=FCMAX002) Set to Y if Any of FCMORSCD = ZZY for a subject; Set to N otherwise
Time	VASOI	Vasopressor, Inotrope or other Vasoactive agent by Study Day (Binary Y/N)	DMDATA.FACM (Where FCMTSTCD=FCMAX002) Treat any Screening results as being from Day 1 (use the worst case outcome as Day 1 result). For each subject and visitnum match: Set corresponding VASOI to Y if FCMORSCD = ZZY for Day ; Set to N otherwise
Subject	PRONEX	Proned at any time (Binary Y/N)	ARDATA.PR (Where PRTREAT=MECHANICAL VENTILATION; exclude records with PRREFID=SOFA) Set to Y if Any of Subjects records have PRONE=Y

Type	Variable Name	Details	Suggestions for derivation / data source
Time	PRONEI	Proned by Study Day (Binary Y/N)	ARDATA.PR (Where PRTREAT=MECHANICAL VENTILATION & VISITNUM in (20,30,40); exclude records with PRREFID=SOFA) For each subject and visitnum match: Set corresponding PRONEI to Y if PRONE = Y for Day ; Set to N otherwise
Subject	ECMOX	ECMO at any time (Binary Y/N)	ARDATA.PR (Where PRTREAT= EXTRACORPOREAL MEMBRANE OXYGENATION) Set to Y if Any of Subjects records have PROCCUR=Y
Time	ECMOI	ECMO by Study Day (Binary Y/N)	ARDATA.PR (Where PRTREAT= EXTRACORPOREAL MEMBRANE OXYGENATION & VISITNUM in (20,30,40)) For each subject and visitnum match: Set corresponding ECMOI to Y if PROCCUR = Y for Day ; Set to N otherwise
Subject	ECCO2RX	ECCO2R at any time (Binary Y/N)	ARDATA.PR (Where PRTREAT= EXTRACORPOREAL CO2 REMOVAL) Set to Y if Any of Subjects records have PROCCUR=Y
Time	ECCO2RI	ECCO2R by Study Day (Binary Y/N)	ARDATA.PR (Where PRTREAT= EXTRACORPOREAL CO2 REMOVAL & VISITNUM in (20,30,40)) For each subject and visitnum match: Set corresponding ECCO2RI to Y if PROCCUR = Y for Day ; Set to N otherwise
Subject	LCOND ^T	Last Contact Date (Date)	ARDATA.DS (Where DSSCATCD=4 & VISITNUM=0) Select DSSTDT

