10.7.2. Handling of Missing Data

Element	Reporting Detail
General	
 Missing data occurs when any requested data is not provided, leading to blank fields on the collection instrument: 
 These data will be indicated by the use of a “blank” in participant listing displays. Unless all data for a specific visit are missing in which case the data is excluded from the table. Answers such as “Not applicable” and “Not evaluable” are not considered to be missing data and should be displayed as such.
Outliers	
 Any participants excluded from the summaries and/or statistical analyses will be documented along with the reason for exclusion in the clinical study report.
Missing Categorical Covariates	
 In the statistical models of RAS peptides as predictors of measures of RV function (and other associated models), a number of categorical covariates (e.g. sex, prior history of RAS modulators, type of echocardiogram, use of vasopressors, proning status, use of nitric oxide) may be required. The following rules should be applied to variables that are to be included in the final statistical model: 
 In the unlikely event that sex is not recorded for a participant, then data from that participant will not be included. For prior history of RAS modulators, a participant is assumed not to have had such a history unless explicitly reported otherwise. For the other variables listed above, which are recorded on each study day, the following imputation algorithm should be applied for missing values: 
 If the same variable is not missing on a previous study day (including screening, if applicable), impute the most recent known value. Otherwise, if the same variable is not missing on a subsequent study day, impute the value from the nearest time point after the missing one. Otherwise, keep the value as missing and exclude the participant from the analysis

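### SAP Table 9 turns a blank day-level vasopressor, nitric oxide or proning answer into No, so the missing-data rule of SAP 10.7.2 has nothing to act on if the table is programmed as written

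*SAP*

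**What the plan says.** SAP 5.3.1 and 10.6.10 set up one dataset, ARDATA.ALLCVTS, to hold the candidate covariates for model building. It has a row for each participant and visit with an evaluable PASP or RV size ratio. Table 9 defines the day-level treatment flags as binary:

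- VASOI (vasopressors): "Set corresponding VASOI to Y if FCMORSCD = ZZY for Day"
- INOI (inhaled nitric oxide): "Set corresponding INOI to Y if FCMORSCD = ZZY for Day"
- PRONEI (proning): "Set corresponding PRONEI to Y if PRONE = Y for Day"
- ECMOI: "Set corresponding ECMOI to Y if PROCCUR = Y for Day", with ECCO2RI built the same way

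Each ends with "Set to N otherwise". None has a missing level. VASOI and INOI take a screening result into Day 1, using the worse of the two. PRONEI, ECMOI and ECCO2RI read only Days 1 to 3.

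Three other places in the SAP deal with missing values:

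- **Section 10.7.2** covers categorical covariates in the final model and names vasopressors, proning and nitric oxide. Its first step is: "If the same variable is not missing on a previous study day (including screening, if applicable), impute the most recent known value". Failing that, the nearest later day is used. Failing that, the value stays missing and the participant is excluded.
- **Section 2.1** covers items added by protocol amendment 2, ECMO and ECCO2R among them. For the two subjects recruited under amendment 1, "the default will now be to leave any data as missing/not applicable".
- **Section 7.1.4** drops the affected time point when a variable required for the primary analysis is missing.

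**The concern.** The SAP gives incompatible instructions for the same blank cell. Under Table 9 it is No. Under 10.7.2 it is imputed from another day or leads to exclusion. Nothing in the SAP says that imputation is done on source data before the default to No.

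If Table 9 is followed literally, some treated days are filed as untreated. SAP 7.1.1 lists vasopressors fourth, proning sixth and nitric oxide eighth of 14 potential covariates, in order of expected importance. Should any of them enter the final model, misfiled days would weaken the adjustment of the Ang II slope. If Table 5.3 (summaries by categorical covariate, used to decide which covariates to include) is drawn from this dataset, the No row would also contain days of unknown status, and the contrast between rows would shrink.

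For ECMO and ECCO2R, the two amendment 1 subjects would be shown as No on questions that their version of the protocol did not ask.

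**Working it through.** **Step 1. One blank cell, followed through the text.** Take a participant with an evaluable echocardiogram on Day 2, vasopressor status Yes on Day 1, and a record for Day 2 with the answer blank.

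| Rule | Day 2 value |
|---|---|
| Table 9 as written | No |
| 10.7.2 | Yes, carried from Day 1 |
| 7.1.4, if it covers covariates | Day 2 dropped |

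The first two cannot both hold. Once the cell is No, 10.7.2 cannot detect it. Table 9 is able to keep an unknown state: in-hospital mortality is coded Yes, No or Unknown.

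**Step 2. Stated figures.** No figure in either document depends on this coding. The sample-size simulations in protocol Appendix 5 contain no covariates.

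**Step 3. Illustrative size.** All inputs here are assumptions. A binary confounder V has prevalence p. It shifts log Ang II and the outcome by 1 within-group SD each, and Ang II itself has no effect. A share m of day records is missing, unrelated to V. W is the recorded flag.

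- c = p(1 − p); crude slope = c/(1 + c)
- R = cov(V,W)²/var(W); adjusted slope = (c − R)/(1 + c − R)
- Missing-as-No: P(W=1) = p(1 − m); var(W) = p(1 − m)[1 − p(1 − m)]; cov(V,W) = p(1 − m)(1 − p)
- Carry-forward, where 90% of users were also users the day before: var(W) = p(1 − p); cov(V,W) = p(1 − m + 0.9m) − p²

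Worked case, p = 0.5 and m = 0.10. Crude slope = 0.25/1.25 = 0.200.

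- Missing-as-No: var(W) = 0.45 × 0.55 = 0.2475; cov = 0.45 × 0.5 = 0.225; R = 0.0506/0.2475 = 0.2045; adjusted slope = 0.0455/1.0455 = 0.0435, which is 21.7% of 0.200.
- Carry-forward: cov = 0.5 × 0.99 − 0.25 = 0.245; R = 0.0600/0.25 = 0.2401; adjusted slope = 0.0099/1.0099 = 0.0098, which is 4.9% of 0.200.

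Share of crude confounding left after adjustment, p = 0.5:

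| Missing | Missing-as-No | Carry-forward |
|---|---|---|
| 0% | 0% | 0% |
| 2% | 4.9% | 1.0% |
| 5% | 11.6% | 2.5% |
| 10% | 21.7% | 4.9% |
| 20% | 38.5% | 9.6% |

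At 10% missing, the pair is 16.1% against 3.4% at 30% prevalence, and 30.9% against 7.8% at 70% prevalence.

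**Step 4. Table 5.3.** Under the same assumptions, true users make up pm/[1 − p(1 − m)] of the No row, and the Yes-minus-No contrast shrinks by that fraction. At p = 0.5 and m = 0.10 this is 0.05/0.55 = 9.1%; at m = 0.02 it is 0.01/0.51 = 2.0%.

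**The case against.** The case against making much of this has several parts, and most of them stand.

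- **Table 9 is guidance.** It is labelled as suggested metadata that may be modified, and the final specification sits elsewhere. A reader might infer that 10.7.2 can never apply. The documents do not support that, because a programmer could impute from source first. What stands is that no text tells them to.
- **Absent records may be safe.** The rules work on matched participants and visits, so a wholly absent record might stay missing after the merge. A blank answer in an existing record still becomes No.
- **There are safeguards.** VASOI and INOI use screening for Day 1. The schedule ties vasopressor, status and management recording to each echocardiogram. A visit without an evaluable PASP or RV size ratio creates no row. Missingness may therefore be low. Days 2 and 3 have no fallback.
- **ECMO and ECCO2R are not named in 10.7.2.** A reader might infer that they fall under it. Their documented conflict is with 2.1 and concerns two subjects, and 2.1 adds that those exploratory endpoints will not be analysed further. Section 7.1.1 nevertheless still lists both as potential covariates.
- **The covariates may never be used.** The initial model has nine parameters and none of these flags. Age and sex would be added first, and 7.1.1 says that covariate exploration may not happen. A reader might infer that the primary analysis is left confounded by this coding. That does not follow unless the flags enter the final model and true users have blank records.
- **Table 5.3 has a looser link.** The SAP does not name ALLCVTS as its source, and 10.7.2 covers only final-model variables. The distortion arises only if the table is built from these flags.

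**Conclusion.** The inconsistency is real and specific. Programmed as written, Table 9 records a blank vasopressor, nitric oxide or proning answer as No, and 10.7.2 then has nothing to impute or exclude. The same default for ECMO and ECCO2R contradicts 2.1 for two subjects.

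The consequence is conditional. It needs blank answers on treated days, and it needs the covariate to be in the final model or in a Table 5.3 built from this dataset. The sizes rest on assumed prevalence, effect sizes, persistence and missing rate, with missingness unrelated to treatment. At 2% missing the loss is small, about 5% of the crude confounding. At 10% to 20% it is about 22% to 38%, roughly four times what carry-forward leaves. The documents do not show where in that range the study lies. The point merits correction because the result would otherwise depend on an undocumented programming choice and the remedy is cheap.

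**What to change.** 1. In Table 9, set VASOI, INOI, PRONEI, ECMOI and ECCO2RI to N only on an explicit negative code, and to missing otherwise.
2. State that 10.7.2 is applied after this step to any of its variables that enter the final model, using screening values where they were collected.
3. State whether ECMO and ECCO2R fall under 10.7.2, and reconcile that with the leave-missing default in 2.1.
4. Reconcile 10.7.2 with 7.1.4, saying whether a missing covariate removes the time point or the participant.
5. Set the any-time flags to N only when every attended study day has an explicit or imputed No. One No plus blank days is not enough.
6. Report the number of imputed values for each covariate.

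The cost is a few lines of derivation text and code, and possibly a few participants or days lost from covariate models. No new data are needed.

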7.2. Secondary Efficacy Analyses

7.2.1. Endpoint / Variables

The variables to be included in the secondary pharmacodynamic analysis are the same as for the primary pharmacodynamic analysis, with the addition of the following independent variables:

- Ang(1-7) on Study Days 1, 2 and 3
- (Optionally) Ang(1-5) on Study Days 1, 2 and 3 (if the correlation between Ang(1-7) and Ang(1-5) values is not too high – otherwise the analysis would not be expected to add additional insights/value)
- Note: The planned modelling using similar techniques to the primary analysis for the Ang II/Ang(1-7) response on Study Days 1, 2 and 3 will not be attempted.

Incidence rates would be assessed across

- i) the entire study (the outcome taking the value of the worst case observed) and
- ii) on an individual visit basis (Note: Screening and Day 1 data would be combined and labelled as Day 1; the worst case outcome used in any combination)

The following rates would be assessed

- Incidence rates of ARDS diagnosis
- Incidence rates of PCD or ACP (any right ventricular dysfunction; regardless of PCD or ACP severity level)
- Incidence rates of PCD (Moderate PCD (not severe enough to qualify as ACP))
- Incidence rates of Non-severe ACP
- Incidence rates Severe ACP

Additionally, the worst case PCD/ACP diagnosis across the study would be combined with the ARDS diagnosis to form the following categories

- ARDS and No PCD or ACP
- ARDS and PCD
- ARDS and Non-Severe ACP
- ARDS and Severe ACP

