Subject	LCONDY	Last Contact Study Day (Continuous)	ARDATA.DS (Where DSSCATCD=4 & VISITNUM=0) Select DSSTDY
Subject	FUDT	Date of Follow Up Visit (Date)	DMDATA.VISIT (Where VISITNUM=50) Select VISITDT

Type	Variable Name	Details	Suggestions for derivation / data source
Subject	DTHHOSP	In hospital mortality (Categorical Y/N/U)	DMDATA.SS (Where VISITNUM=50 & SSTESTCD=AD009) Set to Y if SSORRSCD=ZZY; to N if SSORRSCD=ZZN and to U if SSORRSCD=ZZUNK
Subject	DERDTHDT	Derived Death Date (Date)	Set to the earliest of the dates obtained from... DMDATA.DTH (match on SUBJID and select DDDT) Or LCOND variable if DTHHOSP = Y Or If no dates located above but subject has DMDATA.STATUS DTHBWIN=Y then set to a derived date corresponding to day 3 (relative to that subjects date of 1 st echo) Otherwise set to missing
Subject	DERDTHDY	Derived Death Study Day (Continuous)	The study day of the DERDTHDT (relative to time zero – the date of 1 st echo) Set to missing if DERDTHDT = missing
Subject	DTH28	Death by Day 28 (Categorical Y/N/U)	Set to Y if DERDTHDY not missing & \leq 28 Set to N if [DERDTHDY = missing & LCONDY \geq 28] or [DERDTHDY \geq 28] Set to U otherwise
Subject	SURVIND	Survival Censoring Indicator (Categorical)	Set to 0 if DERDTHDT not missing Set to 1 (censored time) otherwise <Note: Indicator variable should be used in conjunction with LCONDY in any time to event analyses>
Subject	ICUDY	Length of stay (days) in ICU (Continuous)	DMDATA.HRU (Where HUCLVCD=4) Select HUNDYCAR
Subject	HOSPDY	Length of stay (days) in Hospital (Continuous)	DMDATA.HRU (Where HUCLVCD=8) Select HUNDYCAR

Type	Variable Name	Details	Suggestions for derivation / data source
Subject	DYWVNT	Ventilation Free Days (1 to 28) (Continuous)	DMDATA.HRU (Where HUSCATCD=3) Select DYWVNT
Subject	SGX1TO3	Any Surgery between Day 1 and Day 3 (Binary Y/N)	DMDATA.SURGERY (Where VISITNUM=50) Select SPYN
Time	RVDYSI	Single variable capturing RV Dysfunction Status by Study Day (Categorical: 1=No PCD 2=Moderate PCD (not severe enough to qualify as ACP) 3 = Non-severe ACP 4 = Severe ACP)	ARDATA.CV (Where CVANALFL=1 & CVTSTCD in (AK015, AK016)) For each subject and visitnum match Set to: 
• 1 if CVTSTCD=AK015 & CVORRSCD=N• 2 if [CVTSTCD=AK015 & CVORRSCD=Y] & [CVTSTCD=AK016 & CVORRSCD=51]• 3 if [CVTSTCD=AK015 & CVORRSCD=Y] & [CVTSTCD=AK016 & CVORRSCD=52]• 4 if [CVTSTCD=AK015 & CVORRSCD=Y] & [CVTSTCD=AK016 & CVORRSCD=53]

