Subject	RVDYSX	Single variable capturing Worst observed RV Dysfunction Status at any time (Categorical)	MAX of RVDYSI variable (group by SUBJID)
Subject	PCDACPX	Any PCD or ACP at any time in study (Binary Y/N)	Set to Y if RVDYSX in (2,3,4) Set to N otherwise
Time	PCDACPI	Any PCD or ACP by Study Day (Binary Y/N)	Set to Y if RVDYSI in (2,3,4) Set to N otherwise
Subject	NORVDYSX	Did not have PCD or ACP at any time in study (Binary Y/N)	Set to Y if RVDYSX = 1 Set to N otherwise
Time	NORVDYSI	Did not have PCD or ACP on Study Day (Binary Y/N)	Set to Y if RVDYSI = 1 Set to N otherwise
Subject	PCDX	Worst case was PCD at any time in study (Binary Y/N)	Set to Y if RVDYSX = 2 Set to N otherwise
Time	PCDI	PCD on Study Day (Binary Y/N)	Set to Y if RVDYSI = 2 Set to N otherwise

Type	Variable Name	Details	Suggestions for derivation / data source
Subject	ACPX	Worst case was ACP at any time in study (Binary Y/N)	Set to Y if RVDYSX = 3 Set to N otherwise
Time	ACPI	ACP on Study Day (Binary Y/N)	Set to Y if RVDYSI = 3 Set to N otherwise
Subject	SEVACPX	Worst case was Severe ACP at any time in study (Binary Y/N)	Set to Y if RVDYSX = 4 Set to N otherwise
Time	SEVACPI	Severe ACP on Study Day (Binary Y/N)	Set to Y if RVDYSI = 4 Set to N otherwise
Subject	ARDNOX	ARDS but no PCD or ACP at any time in study (Binary Y/N)	Set to Y if [ARDSX=Y & NORVDYSX=Y] Set to N otherwise
Subject	ARDPCDX	ARDS and worst case PCD at any time in study (Binary Y/N)	Set to Y if [ARDSX=Y & PCDX =Y] Set to N otherwise
Subject	ARDACPX	ARDS and worst case ACP at any time in study (Binary Y/N)	Set to Y if [ARDSX=Y & ACPX =Y] Set to N otherwise
Subject	ARDSACPX	ARDS and worst case Severe ACP at any time in study (Binary Y/N)	Set to Y if [ARDSX=Y & SEVACPX =Y] Set to N otherwise
Time	GII	Global Inhomogeneity Index (Continuous)	DMDATA.CC (Select CCORRSN where CCTESTCD=BY001 & VISITNUM in (20,30,40))

Type	Variable Name	Details	Suggestions for derivation / data source
Time	<Various Vital Signs> SYSBP DIABP HEART TEMP RESP VSPO2BLD VSMAP VSPPV	Take names/properties directly from dataset (Continuous)	DMDATA.VITALS (Where VISITNUM in (20,30,40) & VSREFID ^= SOFA) Select (use same name) SYSBP DIABP HEART TEMP RESP VSPO2BLD VSMAP VSPPV Match on subjid and visitnum
Time	OI	Oxygenation Index (Continuous)	DMDATA.RE (Where VISITNUM in (20,30,40) & RETESTCD=AC002) Select REORRSN Match on subjid and visitnum

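### SAP Table 9 has no branch for a PCD/ACP Yes without a severity code, so the any-PCD/ACP flag defaults to N and the record is left unclassified

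*SAP*

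**What the plan says.** SAP 10.6.10, Table 9, builds the daily status RVDYSI from two echocardiography items: AK015 (is PCD or ACP present) and AK016 (its severity).

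- Level 1, no disease: "1 if CVTSTCD=AK015 & CVORRSCD=N".
- Level 2, moderate PCD: "2 if [CVTSTCD=AK015 & CVORRSCD=Y] & [CVTSTCD=AK016 & CVORRSCD=51". Levels 3 and 4 have the same form with severity codes 52 and 53.
- RVDYSX, the worst status over the study: "MAX of RVDYSI variable (group by SUBJID".
- PCDACPI, any PCD or ACP on the day: "Set to Y if RVDYSI in (2,3,4) Set to N otherwise". PCDACPX, at any time: "Set to Y if RVDYSX in (2,3,4) Set to N otherwise".
- NORVDYSI, no PCD or ACP on the day: "Set to Y if RVDYSI = 1 Set to N otherwise". NORVDYSX, at no time: "Set to Y if RVDYSX = 1 Set to N otherwise".
- ARDNOX is Y when ARDSX and NORVDYSX are both Y.

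Elsewhere, SAP 5.3.2 gives PCDACPX and PCDACPI the meaning that the participant had PCD or ACP. SAP 7.2.1 lists among the secondary rates: "Incidence rates of PCD or ACP (any right ventricular dysfunction; regardless of PCD or ACP severity level". SAP 7.2.2 takes the numerator as the count of Yes responses, without naming a source variable.

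**The concern.** The any-disease question needs one fact: was AK015 answered Yes? Table 9 asks for two, because PCDACPI and PCDACPX are read from a severity scale that an uncoded Yes cannot enter. The catch-all N then gives a recorded Yes the same any-disease value as a recorded No.

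For the any-disease flags the error runs one way: a case can be dropped and none can be added. If a rate were built on them, the case would leave the numerator while the participant stayed in the denominator, because SAP 7.2.2 counts everyone with an ARDS or PCD/ACP assessment. The NORVDYSX flag could be wrongly positive, and through it ARDNOX, which feeds one of the ARDS combinations in SAP 7.2.1. The PCD/ACP columns of Table 1.7 would be affected in the same way if they used these variables.

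**Working it through.** **The plan's own figure.** The only stated precision for an incidence rate is in Protocol 10.1: ACP at 10%, N = 150. The half-width is 1.96 × √(0.10 × 0.90 / 150) = 0.048, which rounds to the stated ±5 points. It reproduces. It concerns ACP, and no figure is given for the any-PCD/ACP rate. The point below does not depend on it.

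**Day level.** Applying the Table 9 rules literally:

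| AK015 | AK016 | RVDYSI | PCDACPI | NORVDYSI |
|---|---|---|---|---|
| No | none | 1 | N | Y |
| Yes | 51, 52 or 53 | 2, 3 or 4 | Y | N |
| Yes | missing | missing | **N** | N |
| missing | missing | missing | N | N |

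An uncoded Yes gets the same two flags as a visit with no assessment. It is not labelled disease-free, because NORVDYSI is also N.

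**Subject level.** I assume that MAX skips missing values, as a SAS-type MAX does.

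| Recorded days | RVDYSX | PCDACPX | NORVDYSX |
|---|---|---|---|
| Uncoded Yes on every recorded day | missing | N | N |
| Uncoded Yes once, plain No on the others | 1 | **N** | **Y** |
| Uncoded Yes once, Yes coded 51 once, No once | 2 | Y | N |

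In the second row a participant with a recorded Yes is flagged as never having PCD or ACP. With ARDSX = Y, ARDNOX is also Y. If MAX returned missing instead, NORVDYSX in that row would be N but PCDACPX would still be N. In the third row the participant is kept in the whole-study flag, although the uncoded day is still N.

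**Other rules.** SAP 10.6.6 sets out blank and not-done handling for other echocardiography endpoints, but not for AK015 or AK016. SAP 10.7.2 has no rule for a missing severity code.

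**Size, by illustration only.** Neither the any-PCD/ACP rate nor the share of uncoded Yes answers is in the documents, so both are assumed. Let q be the share of true cases whose recorded Yes answers are all uncoded. If Table 4.1 used PCDACPX, the reported rate would be (cases − lost) / N. For N = 150, with lost cases rounded to whole participants:

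| True rate (cases) | q = 5% | q = 10% | q = 20% |
|---|---|---|---|
| 20% (30) | 28/150 = 18.7% | 27/150 = 18.0% | 24/150 = 16.0% |
| 40% (60) | 57/150 = 38.0% | 54/150 = 36.0% | 48/150 = 32.0% |
| 60% (90) | 86/150 = 57.3% | 81/150 = 54.0% | 72/150 = 48.0% |

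The intervals use the Wilson score method with continuity correction named in SAP 7.2.2. The lower limit is [2np + z² − 1 − z√(z² − 2 − 1/n + 4p(n(1 − p) + 1))] / [2(n + z²)]. The upper limit is [2np + z² + 1 + z√(z² + 2 − 1/n + 4p(n(1 − p) − 1))] / [2(n + z²)].

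For 54/150, 2np = 108 and z² = 3.84:
- lower: (108 + 3.84 − 1 − 23.32) / 307.68 = 28.4%
- upper: (108 + 3.84 + 1 + 23.41) / 307.68 = 44.3%

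The same method gives 32.2% to 48.3% for 60/150, 30.3% to 46.3% for 57/150 and 24.8% to 40.2% for 48/150.

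The study stopped early and the documents do not give the final N. At an assumed N of 25, one lost case is 1/25 = 4 points, for example 10/25 = 40.0% becoming 9/25 = 36.0%.

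**The case against.** Four points can be made for the plan, and each has some force.

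**The day is not called negative.** A reader might infer that an uncoded Yes is recorded as no PCD or ACP. The documents do not support that for the day itself: RVDYSI is missing, not 1, and NORVDYSI is N. The false negative label arises only at subject level, when another day is a plain No and no day is coded positive. This stands in full.

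**The secondary rate may not use these flags.** A reader might infer that the reported any-PCD/ACP rate loses cases. The SAP does not say so. Table 9 is introduced as holding covariates for modelling, and the Yes count in SAP 7.2.2 can be read as AK015 = Y. PCDACPI is never missing, so it cannot supply the per-item visit count that SAP 7.2.2 needs. Table 9 rows are also limited to visits with an evaluable PASP or RV size ratio, whereas the At Risk population can admit participants on a recorded diagnosis alone. On the other side, the rates in SAP 7.2.1 match the Table 9 categories closely, and the SAP gives no other derivation of them. The link is plausible but not established.

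**The trigger may never occur.** The case report form might not allow a Yes without a severity, and data cleaning precedes analysis. No document reports such a record. It is nevertheless conceivable: AK015 and AK016 are separate items, the PCD/ACP distinction in Protocol 9.5.3 turns on septal dyskinesia, and SAP 10.6.6 allows paradoxical septal motion to be not done.

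**Table 9 is open to revision.** It is offered as suggestions, with the final specification held elsewhere. That lowers the priority, but the rule as written still gives the wrong value.

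**Conclusion.** The derivation gap is real and follows from the text alone. An uncoded Yes yields PCDACPI = N, and PCDACPX = N unless another day has a coded severity. Both conflict with the meaning given to the flags in SAP 5.3.2 and with a rate defined regardless of severity in SAP 7.2.1. NORVDYSX = Y for such a participant further requires a plain No on another day, no coded positive on any day, and a MAX that skips missing values.

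Any rate, subgroup or Table 1.7 column built on these flags can lose recorded cases. Whether any are lost, and how many, cannot be determined: the documents give neither the frequency of uncoded Yes answers nor the source of Table 4.1. The rates in the illustration rest on assumed inputs and mainly return the assumed share, so they are not evidence that the loss matters. Priority: minor.

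**What to change.** In Table 9, take the any-disease flags from AK015:

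- PCDACPI = Y if AK015 = Y, N if AK015 = N, missing otherwise.
- PCDACPX = Y if any day has AK015 = Y.
- NORVDYSI = Y only if AK015 = N on that day.
- NORVDYSX = Y only if at least one day has AK015 = N and no day has AK015 = Y.

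Leave RVDYSI and RVDYSX as they are for the severity rows. Do not add an RVDYSI level for severity not recorded: RVDYSX is a maximum, so a level coded above 4 would displace severe ACP. Hold that state in a separate flag and footnote its frequency in Table 4.1.

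Name the revised flags as the source of the any-PCD/ACP row in Table 4.1 and of the PCD/ACP columns in Table 1.7. For Table 4.1, make sure that they cover every visit with an AK015 answer, including visits without an evaluable PASP or RV size ratio.

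Records with AK015 = N, or with a coded Yes, keep their daily flags. An uncoded Yes moves from N to Y on PCDACPI, and a missing AK015 moves from N to missing, which also allows assessed visits to be counted. The cost is a few lines of derivation text and code, with no new data. The downside is that the severity rows may no longer sum to the any-PCD/ACP row, which the footnote explains.
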